EP	Enrolled Population
ESR	Erythrocyte Sedimentation Rate
EudraCT	European Union Drug Regulating Authorities Clinical Trials Database
FDA	Food and Drug Administration
FiO ₂	Fractional Inspired Oxygen
GCP	Good Clinical Practice
GFR	Glomerular filtration rate
HFNC	High-Flow Nasal Cannula
HIT	Heparin Induced Thrombocytopenia
HIV	Human Immunodeficiency Virus
hsCRP	high-sensitivity C-reactive protein
IB	Investigators' Brochure
ICH	International Council for Harmonisation
ICU	Intensive Care Unit
IDMC	Independent Data Monitoring Committee
IEC	Independent Ethics Committee
Ig	Immunoglobulin
IL	Interleukin

IMP	Investigational Medicinal Product
IMV	Invasive Mechanical Ventilation
IND	Investigational New Drug
INR	International Normalized Ratio
IRB	Institutional Review Board
ITP	Immune Thrombocytopenia
ITT	Intent-To-Treat
IV	Intravenous
IVIG	Intravenous Immunoglobulin
KDIGO	Kidney Disease Improving Global Outcomes
LAR	Legally Authorized Representative
LDH	Lactic acid dehydrogenase
LOCF	Last Observation Carried Forward
MedDRA	Medical Dictionary for Regulatory Activities
MERS	Middle East Respiratory Syndrome
MIS	Multisystem Inflammatory Syndrome
MMN	Multifocal Motor Neuropathy
MQoL-SIS	McGill Quality of Life Single-Item Scale
NCI-CTCAE	National Cancer Institute-Common Terminology Criteria for Adverse Events
NIH	National Institutes of Health
NIV	Non-Invasive Mechanical Ventilation
PaO ₂	Arterial Oxygen Partial Pressure
PP	Per Protocol
PT	Prothrombin Time
PTT	Partial Thromboplastin Time
RNA	Ribonucleic acid
RT-PCR	Reverse Transcription Polymerase Chain Reaction
QoL	Quality of Life
SAE	Serious Adverse Event
SAF	Safety Analysis Set
SAP	Statistical Analysis Plan
SARS	Severe Acute Respiratory Syndrome
SARS-CoV-2	Coronavirus 2
SDV	Source Data Verification
SID	Secondary immune deficiency
SmPC	Summary of Product Characteristics
SOC	Standard of Care
SOP	Standard Operating Procedure
TACO	Transfusion-associated circulatory overload
TEE	Thromboembolic Event
TRALI	Transfusion-related acute lung injury

1 INTRODUCTION

Coronaviruses (CoV) are enveloped ribonucleic acid (RNA) viruses capable of causing acute respiratory distress in humans (1). Previous outbreaks have caused Middle East Respiratory Syndrome (MERS/MERS-CoV) and Severe Acute Respiratory Syndrome (SARS/CoV). In December of 2019, a highly infectious coronavirus designated 2019-nCoV causing the severe acute respiratory syndrome from Coronavirus 2 (SARS-CoV-2) was found to be present in a cluster of patients linked via a seafood and wet animal wholesale market in Wuhan, China (2).

Following the initial outbreak in Wuhan, the spread of Coronavirus disease-2019 (COVID-19) via human to human transmission forced the World Health Organization to declare a global pandemic on March 11, 2020 (3).

In an early description of 41 patients admitted to a hospital in Wuhan and found to be COVID-19 positive, the clinical manifestations showed men were affected three times as often as women. Furthermore, diabetes (20%), hypertension (15%) and other cardiovascular disease (15%) were found to be the most commonly associated diseases (4). Common initial symptoms were fever (98%), dry cough (76%), shortness of breath (55%), and myalgia or fatigue (44%) (4). Median time from symptom onset to dyspnea is 8 days. All patients had lymphopenia and abnormal chest computerized tomography (CT) findings. Adult Respiratory Distress Syndrome occurred in 29%; 15% of all patients died (4).

Risk of death is highest in patients with advanced age, with approximately 80% of deaths occurring among adults older than 60 years of age (5). The main cause of death is massive alveolar damage and progressive respiratory failure caused by inflammatory infiltration of the pulmonary interstitials resulting in pulmonary fibrosis (6).

The proximate cause of death implicates an abnormal pulmonary immune response associated with multiple respiratory viral infections in which there is an elevation of cytokine and chemokine production often associated with poor clinical outcomes, referred to as a "cytokine storm" (7, 8). In patients with severe COVID-19, there is increased interleukin (IL-2, IL-7), granulocyte colony stimulating factor, interferon gamma, inducible protein 10, monocytes chemoattractant protein 1, macrophage inflammatory protein 1-alpha, and tumor necrosis factor-alpha. Elevated IL-6, C-reactive protein (CRP) and myoglobin are significantly associated with patients who die compared to those who are ultimately discharged (7).

There is no known effective treatment for patients infected with COVID-19. Many therapies have been proposed based on anecdotal reports including hydroxychloroquine and azithromycin (9), corticosteroids (10), broad spectrum antiviral agents (11), convalescent plasma (12), and intravenous immunoglobulin (IVIG) (6). IVIG, which consists of pooled IgG preparations from thousands of donors and has

been used to treat patients with immune mediated diseases for almost 40 years (13), is an attractive possible treatment. The adverse effect profile is well understood, as is its most efficacious dose (2 g/kg over 4-5 days) and expected time efficacy (2 to 10 days; personal communication; after 2-3 doses) (14). The mechanism by which IVIG modulates the immune system is uncertain, but among possibilities includes blocking and modulation of Fc expression and signaling, increased autoantibody clearance by FcRn saturation, suppression of immunoglobulin production, modulation of antigen presenting cell activation, blockade of complement proteins, induction of regulatory T cells, and inhibition of differentiation and maturation of dendritic cells (14). Recent studies in patients with idiopathic thrombocytopenia purpura and Guillain-Barre syndrome show that IVIG significantly modulates inflammatory cytokines (15, 16).

Side effects of IVIG include increased blood viscosity, thromboembolic phenomena, acute renal failure, increased blood pressure, and anaphylaxis (14, 17, 18).

The published cases of IVIG showing an effect in patients with COVID-19 infection showed an almost immediate impact on disease progression after receiving a standard loading dose of IVIG (2 g/kg over 5 days), enabling discharge within 10 days of IVIG initiation (6). None were intubated, but all were treated while being observed to have increasing dyspnea and decreasing oxygen saturation levels. All had markedly elevated high sensitivity CRP (hsCRP) and abnormal CT scan (6).

1.1 Rationale for Conducting the Study

In early 2020, several case studies were published which showed the successful use of IVIG in treating COVID-19 patients (6, 19, 20, 21, 22). A retrospective, multicenter cohort study that included 325 adult critical patients from 8 centers, demonstrated that early high-dose IVIG administration (<7 days following admission) improves the prognosis of critical COVID-19 patients (19). In addition, a retrospective chart review of 58 patients with severe COVID-19 pneumonia compared outcomes in those receiving high-dose IVIG treatment ≤ 48 hours versus > 48 hours after admission to the intensive care unit (ICU). Results demonstrated that high-dose IVIG received ≤ 48 hours after admission to the ICU resulted in reductions in the use of mechanical ventilation, hospital/ICU stay, and 28-day mortality in patients with severe COVID-19 pneumonia (20). An observational study was conducted in 10 COVID-19 patients, and results demonstrated that short-term moderate-dose corticosteroid combined with high-dose IVIG effectively reversed severe, deteriorating COVID-19 patients who failed initial low-dose therapy (21). It's notable that researchers were motivated to employ this therapeutic regimen as it was preliminarily shown to reduce the risk of death in 12 patients with SARS. The authors postulate that corticosteroid use at an early deterioration stage has a timely effect on the suppression of the inflammatory response. More importantly, the combination use of IVIG is believed to strengthen

immune function to prevent a potential delay in viral clearance caused by the corticosteroid.

Another study conducted in three deteriorating patients with severe COVID-19 who received high-dose IVIG (0.3 to 0.5 g/kg/day for 5 days) demonstrated that all experienced a successful recovery with significant improvement in symptoms within 24 to 48 hours. They also observed that “the first few days of deterioration may present a critical point when potent suppression of the inflammatory cascade could save patients from fatal immune-mediated injuries.” (6).

More recently, Sakoulas et al. have performed a prospective randomized controlled pilot study in 34 COVID-19 patients (22). Sixteen patients received IVIG (0.5 g/kg/day for 4 days) plus standard of care (SOC) versus 17 patients SOC alone. Among subjects with A-a gradient of >200 mm Hg at enrollment, the IVIG group showed i) a lower rate of progression to requiring mechanical ventilation (2/14 vs 7/12, $p=0.038$ Fisher exact test), ii) shorter median hospital length of stay (11 vs 19 days, $p=0.01$ Mann Whitney U), iii) shorter median ICU stay (2.5 vs 12.5 days, $p=0.006$ Mann Whitney U), and iv) greater improvement in $\text{PaO}_2/\text{FiO}_2$ at 7 days (median [range] change from time of enrollment +131 [+35 to +330] vs +44.5 [-115 to +157], $p=0.01$, Mann Whitney-U) than SOC. No safety signals including thrombo-embolic events were detected.

The benefits of IVIG in COVID-19 was further demonstrated in pediatric patients who developed Kawasaki-like disease, also called MIS (Multisystem Inflammatory Syndrome) (23, 24, 25, 26) In Feldstein et al., which documents the largest cohort of patient, 186 patients with MIS were treated in 26 states in the United States and 77% were treated successfully with IVIG (23).

There are documented case studies of IVIG being used in patient care for various viral infections affecting the upper respiratory system (27). In both the United States and Saudi Arabia, varying levels of IVIG were used in the treatment of patients who had been diagnosed with MERS (28). Additionally, various forms of IVIG have been related to symptom improvement in patients diagnosed with SARS (29). Namely, delayed administration of pentaglobin, an IgM-enriched IVIG serum, led to improved radiological appearance and overall improved symptoms in 12 severe SARS patients (30).

Furthermore, IVIG has been seen to have therapeutic effects in a variety of patients with influenza. A 2016 study carried out on immunocompromised children diagnosed with 2009 Influenza (H1N1) concluded that high-dose IVIG could be useful as an ancillary therapy for the influenza virus (31). Likewise, IVIG given at 0.4g/kg over a period of 4 hours, was shown to contribute to decreasing viral loads in adult patients diagnosed with the H1N1 virus (32). In non-human populations, a 2017 study carried out in ferrets demonstrated that IVIG administered at exposure to the influenza virus

(H1N1/H5N1) led to a significant reduction in lung viral load. The study went on to conclude that IVIG administered before the onset of a pandemic had the potential to modulate serious influenza infection-associated mortality and morbidity, and that it could be used as a prophylactic to protect vulnerable populations in the event of a pandemic (33).

IVIG was first introduced in the US for the treatment of primary immune deficiency in the early eighties, it has increasingly been recognized not only for its ability to fight infections but also for its anti-inflammatory and immunomodulatory effects. Other US Food and Drug Administration (FDA) approved indications for IVIG include SID (secondary immune deficiency) CIDP (Chronic inflammatory demyelinating polyneuropathy), MMN (Multifocal Motor Neuropathy), Kawasaki disease and ITP (Immune Thrombocytopenia). IVIG has been studied for decades in numerous different diseases and has a good safety profile.

The mechanism of action of IVIG is not completely understood, but it may modulate the immune response via multiple mechanisms, including blocking a wide array of proinflammatory cytokines that potentially lead to severe inflammatory responses, including cytokine storm, as well as Fc-gamma receptor binding of activated macrophages and other antigen presenting cells.

Recently convalescent plasma was approved for Emergency Use Authorization in COVID-19 patients, although the National Institutes of Health (NIH) has stated that convalescent plasma should not be considered as SOC. There are no randomized prospective trials for convalescent plasma available and no control group was included in these studies. There are potential safety issues of convalescent plasma such as transmission of viruses, TACO and TRALI unlike IVIG which has been pathogen inactivated. One other difference between IVIG and convalescent plasma is the much higher Ig levels in IVIG as compared to convalescent plasma (~40 fold higher) which could result in greater benefits. In conclusion, the preliminary positive IVIG data warrants a larger prospective double-blind, placebo controlled to show efficacy and safety of *Octagam 10%* therapy in COVID-19 patients with severe disease progression.

The study will be conducted in compliance with the protocol, International Conference on Harmonisation-Good Clinical Practice (ICH-GCP), US FDA Code of Federal Regulations (CFR), and other local regulatory requirements.

1.2 Benefit-Risk Statement

The risks of IVIG administration are well documented. In general, the incidence of adverse events (AEs) associated with IVIG tends to increase with the rate of infusion, and thus the recommended dosage, infusion rates, and monitoring procedures should

be adhered to. Patients that are naïve to IVIG are more at risk than those that are well-maintained and on regular therapy.

Patients with pre-existing risk factors for thrombotic events (such as advanced age, obesity, hypertension, diabetes mellitus and a history of vascular disease or thrombotic episodes, patients with acquired or inherited thrombophilic disorders, patients with prolonged periods of immobilization, severely hypovolemic patients, and patients with diseases which increase blood viscosity) may be at increased risk of developing thromboembolic events (TEEs) (34). Overdose is possible in overweight and elderly patients and in those who have impaired renal function. In patients with signs of cerebral or cardiac ischemia, the increase in viscosity caused by an immunoglobulin infusion may be a risk (34).

The safety profile of *Octagam 10%* based on clinical studies and long-term post-marketing experience is well-documented and detailed in the European Summary of Product Characteristics (SmPC) (35). Adverse drug reactions (ADRs) such as chills, headache, dizziness, fever, vomiting, allergic reactions, nausea, arthralgia, low blood pressure, and moderate low back pain occur occasionally. These adverse effects are mostly transient and mild. However, some very rare adverse effects, including renal impairment, thrombosis, arrhythmia, aseptic meningitis, hemolytic anemia, and transfusion-related acute lung injury, are serious (36). AEs are rarely disabling or fatal, treatment involves supportive measures, and the majority of affected patients have a good prognosis. Reactions to IVIGs tend to be related to the dose and the rate of infusion. Rarely, human normal immunoglobulins may cause a sudden fall in blood pressure and, in isolated cases, anaphylactic shock, even when the patient has shown no hypersensitivity to previous administration. Cases of reversible aseptic meningitis and rare cases of transient cutaneous reactions have been observed with human normal immunoglobulin. Reversible hemolytic reactions have been observed in patients, especially those with blood groups A, B, and AB.

For *Octagam 10%*, the same type of adverse reactions has been seen as for other IVIG products. No new or unknown safety problems are expected to emerge which are not already described in the SmPC. In the very limited number of COVID-19 cases treated with IVIG, no new or unknown safety concerns were reported (6).

Based on the severe conditions of COVID-19 patients, we postulate that *Octagam 10%* treatment in COVID-19 patients outweighs potential disadvantages of IVIG.

This trial will be conducted in accordance with local and national COVID-19 safety guidelines. This trial was designed with flexibility for remote telemedicine visits where possible to minimize the risk of exposure of patients and healthcare professionals to COVID-19.

2 STUDY OBJECTIVES

2.1 Primary Objective

- To determine if high-dose *Octagam 10%* therapy will stabilize or improve clinical status in subjects with severe COVID-19 during the first seven days following treatment commencement.

2.2 Secondary Objectives

Key Secondary Efficacy Objectives

- To compare the length of hospital stay in subjects treated with *Octagam 10%* compared to those that received placebo through Day 33.
- To determine if high-dose *Octagam 10%* therapy will stabilize or improve clinical status in subjects with severe COVID-19 during the 14 days following treatment commencement.
- To compare the cumulative duration of invasive mechanical ventilation (IMV) in subjects treated with *Octagam 10%* compared to those that received placebo through Day 33.
- To compare the cumulative incidence of severe progression in subjects treated with *Octagam 10%* compared to those that received placebo at Day 33.
- To compare the length of time in ICU in subjects treated with *Octagam 10%* compared to those that received placebo at Day 33.
- To compare cumulative mortality in subjects treated with *Octagam 10%* compared to those that received placebo at Day 33.

Other Secondary Efficacy Objectives

- To determine if high-dose *Octagam 10%* affects severe acute respiratory syndrome from Coronavirus 2 (SARS-CoV-2) infection status at Day 7.
- To compare the cumulative incidence of new ICU admittance in subjects treated with *Octagam 10%* compared to those that received placebo at Day 33.
- To determine if high-dose *Octagam 10%* therapy will improve clinical status in subjects with severe COVID-19 during the 14 days following treatment commencement.
- To compare the cumulative incidence of IMV in subjects treated with *Octagam 10%* compared to those that received placebo through Day 33.
- To compare the time to recovery in subjects treated with *Octagam 10%* compared to those that received placebo through Day 33.

- To compare the time to first improvement in clinical status in subjects treated with *Octagam 10%* compared to those that received placebo through Day 33.

Secondary Safety Objective

- To describe the safety of *Octagam 10%* compared to placebo when administered to subjects with severe COVID-19.

2.3 Exploratory Objectives

- To compare changes in SpO₂ on room air from Baseline (Day 1) to all available on-study time points up to Day 33 in subjects treated with *Octagam 10%* compared to those that received placebo.
- To compare changes in the Modified Borg Dyspnea Scale from Baseline (Day 1) to Days 7, 14, 21, and 33 in subjects treated with *Octagam 10%* compared to those that received placebo.
- To compare changes in Quality of Life (McGill Quality of Life Single-Item Scale, MQoL-SIS) score from Baseline (Day 1) to Days 7, 14, 21, and 33 in subjects treated with *Octagam 10%* compared to those that received placebo.

Property of Octapharma. Do not copy or distribute without written permission.

3 INVESTIGATIONAL PLAN

This is a Phase 3 randomized, double-blind, placebo-controlled, study of *Octagam 10%* in COVID-19 subjects.

3.1 Primary and Secondary Endpoints

3.1.1 Primary Endpoint

- Proportion of subjects with stabilized or improved clinical status at Day 7 of at least one category on a 6-point clinical status scale.

Clinical status categories will be defined as:

1. Hospital discharge or meet discharge criteria (discharge criteria are defined as clinical recovery, ie, no fever, respiratory rate, oxygen saturation return to normal, and cough relief).
2. Hospitalization, not requiring supplemental oxygen.
3. Hospitalization, requiring supplemental oxygen (but not non-invasive mechanical ventilation (NIV)/high-flow nasal cannula [HFNC]) as defined by A-a Gradient <150 mmHg.
4. ICU/hospitalization, requiring NIV/HFNC therapy, as defined by A-a Gradient \geq 150 mmHg.
5. ICU, requiring extracorporeal membrane oxygenation (ECMO) and/or IMV.
6. Death.

A subject meets the success criteria of stabilization or improvement if the clinical status category on Day 7 is not worse than the clinical status category at Baseline (Day 1 prior to IMP infusion).

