4.1.2 Exclusion Criteria

Subjects who meet any of the following criteria are *not* eligible for the study:

1. Existence of other evidence that can explain pneumonia including but not limited to: Influenza A virus, influenza B virus, bacterial pneumonia (as suggested by the combined clinical picture, radiological findings and known laboratory results [eg, elevated procalcitonin >0.5 ng/mL and concomitant neutrophilia]), known fungal pneumonia, suspected fungal pneumonia based on compromised immune system with a history of past fungal infections, noninfectious causes, etc.
2. Known history of serious allergic reactions, including anaphylaxis, to IVIG or its preparation components.
3. Subjects with a history of thromboembolic event (TEE) within the last 12 months, such as deep vein thrombosis, pulmonary embolism, myocardial infarction, ischemic stroke, transient ischemic attack, peripheral artery disease (Fontaine IV).

4. Subjects with an underlying medical condition that can lead to hypercoagulable states and hyperviscosity such as antithrombin III deficiency, Factor V Leiden, Protein C deficiency, antiphospholipid syndrome, and malignancy.
5. Known history of selective IgA deficiency with antibodies against IgA.
6. Subjects with conditions such as human immunodeficiency virus (HIV) infection, known acute or chronic hepatitis B or C (HBsAg positive or HCV RNA PCR positive or currently treated with antivirals), pulmonary fibrosis, heparin induced thrombocytopenia (HIT), and moderate to severe renal dysfunction (per investigator discretion based on estimated glomerular filtration rate [eGFR] <59 mL/min/1.73 m², as defined by KDIGO Clinical Practice Guideline):
 - Moderately reduced GFR (G3a): GFR = 45 to 59 ml/min/1.73 m²
 - Moderately reduced GFR (G3b): GFR = 30 to 44 ml/min/1.73 m²
 - Severely reduced GFR (G4): GFR = 15 to 29 ml/min/1.73 m²
 - Kidney failure (G5): GFR <15 ml/min/1.73 m².
7. Currently requiring invasive mechanical ventilation or having received invasive mechanical ventilation in the last 30 days.
8. Known clinically significant preexisting lung, heart, neuromuscular or other disease that, in the investigator's opinion, would impact the subject's ability to complete study or may confound the study results.
9. Body weight > 125kg.
10. Women who are pregnant or breast-feeding.

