6.1.8 Time Windows Used in this Study, Including Tolerances

In this study, the following time windows and tolerances apply:

Table 2: Time Windows Used in this Study

Time point	Time stated	Tolerance
Screening Visit	24 hours before Visit 1	Max of 26 hours
Visits 1 to 4	Day 1 to 4	None
Visit 5	Day 7 or discharge day	± 1 day
Visit 6 and 7	Days 14 and 21	± 2 days
End of Study Visit	Day 33	± 3 days
Q3 month post-study follow-up	Every 3 months after completion of core trial or early termination	± 14 days

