7.2.2 Oxygenation/Ventilator Status

Oxygenation status and/or ventilation status will be recorded at each scheduled visit, and in between visits if there is a change in status. The following will be captured:

Supportive measure required to maintain oxygen saturation:

- Nasal canula ≤ 4 L/min
- Nasal canula > 4 L/min
- Face mask
- Non-breather face mask
- Non-invasive ventilation
- Invasive mechanical ventilation.

Data will be used to calculate the incidence of invasive mechanical ventilation, duration of invasive mechanical ventilation and other changes in oxygenation status as required.

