9.2.5 Handling of Missing Data

In support of the primary and key secondary endpoints of stabilization or improvement in clinical status the following imputation methods will be used. For subjects with clinical status assessment at Baseline (Day 1) and at least one non-missing post-baseline clinical status assessment, last observation carried forward (LOCF) will be used to

impute the missing data at Day 7. However, if there is available data that otherwise indicates events such as death, ECMO or IMV, ICU admittance, occurred after the last non-missing clinical status assessment but on or prior to Day 7, the clinical status will be imputed according to the worst-case of either the LOCF or the clinical information available. Subjects with missing data at Baseline (Day 1) will be imputed as failure. Subjects with no post-baseline clinical status assessment on or prior to Day 7 will be imputed as failure.

Sensitivity analyses will be implemented by assuming all failure (worst case scenario) if subject has missing data at Baseline (Day 1) or Day 7, and where subjects with missing data are excluded.

Missing data for the outcome of clinical status at Day 14 will be imputed in the same fashion as in primary endpoint.

For the key secondary endpoint involving severe progression (ECMO, IMV, death, ICU admittance), subjects who withdrew early from study prior to Day 33 without evidence of events will be treated as not having the event. Sensitivity analyses will be conducted (1) treating them as failures (having the event at their last study visit) and (2) excluding them from the analyses. An additional analysis of these endpoints will be provided, treating prohibited medication use prior to Day 33 as an event, as well as allowing for status (event or success) without regard to prohibited medication use.

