##### **4.1 Missing Data**

The latest patient status available prior to Day 7 will be used to determine clinical status in the absence of a clinical status assessment. If a death date is prior to Day 7, clinical status at Day 7 will be identified as a 6. Otherwise, if a subject's last status reflects that they were in the ICU and receiving ECMO and/or IMV, clinical status will be imputed as a 5. Otherwise, if a subject's last status reflects that they were in the ICU and not receiving ECMO and/or IMV, clinical status will be imputed as a 4. If the LOCF clinical status value for a patient is higher than these imputed values or if a subject status cannot be derived based on available information on ECMO, IMV, or ICU status, the last observation carried forward (LOCF)

will be used to impute patient values. Subjects with no post-baseline clinical status assessment, or prohibited medication use, on or prior to Day 7 will be imputed as failure.

An imputation analogous to the primary endpoint will be performed for the secondary endpoint of clinical status at Day 14.

For the secondary endpoint length of hospitalization, Subjects who are still hospitalized as of Day 33, subjects with missing end dates due to withdrawal, subjects with unusable end dates due to prohibited medication use, or those who died on/prior to Day 33 will be censored at Day 33. Discharge occurring on or after the start date of prohibited medication use will not be considered an event.

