#### **4.6 Reporting Timeframe of Measurement for Analysis**

For analyses of primary and secondary efficacy endpoints, including clinical status and RT-PCR, the latest observation within any given study day will be used. If the observations for the Day 7 visit falls outside of the 24-hour window of the study day or the Day 14 visit falls outside of the 48-hour window of the study day, the observation will be considered as missing and the imputation described in Section 4.1 will apply as appropriate. Otherwise, unless specifically stated otherwise, analyses will be conducted based on nominal visits.

For summary analyses of efficacy assessment, including oxygenation, oxygen saturation, modified Borg Dyspnea Scale and McGill Quality of Life Single-Item Scale (MQoL-SIS) and safety parameters (including vital signs, clinical laboratory evaluations and chest CT/chest X-ray findings), the latest observation within the study day during treatment period will be used. No imputation will be made for these assessments.

For safety analysis with adverse events, the observation with highest severity within the study day during treatment period will be used. No imputation will be made.

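### An in-window assessment made before Day 7 (or Day 14) stands as the result even when ECMO or IMV by the target day, or death on it, is on record

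*Protocol*

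**What the plan says.** Protocol 3.1.1 defines success "if the clinical status category on Day 7 is not worse than the clinical status category at Baseline". The second key secondary endpoint is defined in the same way at Day 14 (Protocol 9.2.3.2, SAP 14). On the six-point scale, category 5 is ECMO or IMV and category 6 is death. Protocol 4.1.2 excludes anyone "Currently requiring invasive mechanical ventilation or having received invasive mechanical ventilation in the last 30 days", so either category on the target day is normally a failure.

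Protocol Table 2 (6.1.8) times Visit 5 at "Day 7 or discharge day" with a tolerance of one day either way, and Visits 6 and 7 with two days either way.

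SAP 4.6 sets the analysis window. The wording is "If the observations for the Day 7 visit falls outside of the 24-hour window of the study day", with the parallel clause for the next visit: "the Day 14 visit falls outside of the 48-hour window of the study day, the observation will be considered as missing". Observations that are not out of window are analysed under their nominal visit.

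SAP 4.1 opens its derivation with "The latest patient status available prior to Day 7 will be used to determine clinical status in the absence of a clinical status assessment", and SAP 13 sends only missing Day 7 data to that section. Protocol 9.2.5 imputes missing Day 7 status by the worse of the last observation and any event that "occurred after the last non-missing clinical status assessment but on or prior to Day 7".

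Protocol 7.2.2 records oxygenation and ventilator status at each visit and "in between visits if there is a change in status".

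**The concern.** The endpoint is a state on a fixed day, while the analysed value may come from an earlier day. When the early value lies inside the window, nothing is missing, so the rules that would bring in a later known event are not triggered.

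The plan then treats identical Day 7 states differently. Take two subjects in category 4 at baseline, both intubated on Day 7. The first was last assessed on Day 4 and has no Day 7 assessment; Protocol 9.2.5 makes that subject a failure. The second was assessed on Day 6 and scored 4; that score stands and the subject is a success. The only difference is when the site made the visit.

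The same gap exists at Day 14, where an assessment on Day 12 leaves up to two days. A subject could count as stabilised at Day 14 while ventilated, or dead, on that day according to dates used for other key secondary endpoints.

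**Working it through.** **The text, step by step.**
1. Day 6 and Day 12 are allowed visit days (Table 2).
2. If the SAP's 24 and 48 hours mean plus or minus, which matches Table 2, those assessments are in window and not missing (SAP 4.6).
3. SAP 4.1, SAP 13 and Protocol 9.2.5 are all framed for missing status. None replaces a non-missing score.
4. The SAP 13 sensitivity analyses (PP and Safety populations, complete cases, prohibited medication ignored, missing as failure) do not reclassify this subject either.

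**The plan's own figure.** Inputs from Protocol 9.1: success 0.60 on placebo and 0.80 on IVIG, two-sided 0.05, 88 per arm, 15% drop-out. With pooled variance under the null and unpooled under the alternative:

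power = Φ{[0.20 − 1.96 × √(2 × 0.70 × 0.30/88)] / √[(0.24 + 0.16)/88]} = Φ{(0.20 − 1.96 × 0.0691)/0.0674} = 83.1%.

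This agrees with the stated minimum of 80%. Also 88/0.85 = 103.5, so 104 per arm and 208 in total, as stated.

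**Size of the early-side error.** The documents do not give the share of Visit 5 assessments made on Day 6, the timing of failures, or the share of failures that are death or IMV. Assumptions, as ranges:
- s, share assessed on Day 6: 20% to 50%;
- failures spread evenly over the six days from Day 2 to Day 7, so 1/6 fall on Day 7;
- e, share of failures that are death or IMV: 25% to 50%.

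The fraction of failures scored as success is f = s × e/6. The expected count per arm is 104 × failure rate × f. Observed success rates become 0.60 + 0.40f and 0.80 + 0.20f.

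| | Low (s = 0.20, e = 0.25) | High (s = 0.50, e = 0.50) |
|---|---|---|
| f | 0.0083 | 0.0417 |
| Placebo, 104 × 0.40 × f | 0.3 | 1.7 |
| IVIG, 104 × 0.20 × f | 0.2 | 0.9 |
| Difference, 20 × (1 − f) points | 19.8 | 19.2 |
| Power at 88 per arm | 82.6% | 80.8% |

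Counting every failure (e = 1) gives larger figures: at s = 0.50, a difference of 18.3 points and power of 78.2%. That includes moves from category 3 to 4, which are not the events at issue, so it is only an outer bound.

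**Day 14.** If early visits fall on Day 12 and failures are even over 13 days, f = s × e × 2/13, or 0.8% to 3.8%. The plan gives no Day 14 rates, so I do not convert this to counts or power.

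**Late side.** A subject stable on Day 7, intubated on Day 8 and assessed on Day 8 is scored a failure. With even event timing and equal Day 6 and Day 8 shares, the expected shifts in the success rates largely cancel, although individual subjects remain misclassified.

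**The case against.** Five points can be made against the concern.

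- **Deaths before the target day.** SAP 4.1 has a sentence giving category 6 to a subject whose death date precedes Day 7, and it carries no absence-of-assessment condition of its own. Read alone, it would catch a Day 13 death after a Day 12 assessment, since Day 14 is handled analogously. This stands in part: the sentence sits under missing data and SAP 13 routes only missing data there, so such deaths are ambiguous. It does not reach death on the target day itself, or ECMO/IMV.
- **The window.** SAP 4.6 could mean the 24 hours of Day 7 alone. A Day 6 visit would then be missing and the event rules would apply. This is possible, but fits Table 2 less well.
- **Other safeguards.** SAP 1 says the imputation rules were revised to use more subject information at each visit, and SAP 7 leaves final endpoint imputation to blinded review. Either might catch a case, but neither states a rule.
- **Both sides of the window.** Late visits offset early ones on average. This stands, and the fix should cover both.
- **Consequences.** Severe progression and mortality through Day 33 are tested separately as key secondary endpoints. True, but they come later in the hierarchy and do not correct the primary endpoint.

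A reader might infer that all known deaths and other failures before Day 7 count as successes. The documents do not support that: out-of-window and missing assessments go to the event rules, and earlier deaths are arguably covered.

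**Conclusion.** The point holds in a limited form. Under the plus-or-minus reading of SAP 4.6, ECMO/IMV started after an early in-window assessment and in progress on the target day, and death on the target day, are scored as success. Death between the assessment and the target day is unresolved by the text.

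The size is probably small: roughly 0 to 2 subjects per arm for the primary endpoint, a loss of 0.2 to 0.8 points from a 20-point difference, and power at 88 per arm that stays above 80%. This rests on the assumed Day 6 share, even failure timing and the assumed share of failures that are death or IMV. It ignores the partly offsetting Day 8 visits.

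Two stronger inferences are tempting. The first is that the study loses its 80% power; that appears only when failures other than death or IMV are counted and many visits fall on Day 6. The second is that the rule favours IVIG. With the same visit timing in both arms, it hides more failures in the arm that has more of them, so under the plan's rates it attenuates the difference. Nothing in the documents shows visit timing differing by arm.

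Low-to-moderate priority: the numerical effect is minor, but scoring of the primary endpoint should not depend on the visit day when the later event is dated in the database.

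**What to change.** Amend SAP 4.6 and 4.1 before unblinding:

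- Define the windows in study days: Day 7 ± 1 and Day 14 ± 2.
- State that death, or ECMO/IMV in progress, dated on or before the target day sets status to 6 or 5 respectively, whatever an earlier in-window assessment shows.
- State that an event dated after the target day does not set target-day status.
- Use the same cut-off, on or prior to the target day, in the SAP and the protocol. At present SAP 4.1 stops short of Day 7 where Protocol 9.2.5 includes it.

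Protocol 9.2.5 also uses ICU admittance in its worst-case rule. The amendment should say whether that extends to in-window assessments or stays confined to missing status.

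The cost is a few sentences and a small merge of death and ventilation dates that are already collected. A few subjects will change classification, in either direction.
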